7.3 SITE QUALIFICATION

The qualified study center will have experienced researchers familiar with laws, regulations and good clinical practice guidelines applicable to Korea, and interventional radiologist(s)

experienced with the use of microwave and/ or radiofrequency ablation devices in the liver.

Each site must provide all documentation required by the Sponsor's Site Initiation procedure (refer to section 12.2) prior to consenting and enrolling the first subject.

7.4 TRAINING FOR PROSPECTIVE STUDY TREATMENT

All Investigators and staff involved in the ablation procedure must undergo standard device inservicing/ training prior to treatment of first subject. Additional training may be performed at the request of the Sponsor or study staff. Investigators using the study device will be trained on the Instructions For Use (IFU).

All Investigators and those to whom the Investigator delegates study responsibilities will be trained on the protocol by a representative of the Sponsor.

8.0 STUDY POPULATION

Subjects will be selected for recruitment into this study from patients who are scheduled for microwave ablation of the liver in accordance with their institution's SOC, and who meet general study entry criteria. A subject will be considered enrolled after signing the study's informed consent forms (ICFs).

Enrollment will continue until 30 eligible subjects have been treated with Neuwave microwave ablation and have completed the 3-month visit (Visit 4). One center in Korea will be selected as study site. No study-related procedure or form associated with this study can be completed until informed consent is obtained for that Subject.

8.1 INCLUSION CRITERIA

1. Confirmed hepatocellular carcinoma, tumor size of ≥ 2 cm and up to 5 cm, single location, BCLC Stage A based on imaging (CT Scan/ MRI/ ultrasound) and biopsy confirmation in accordance with their institution's SOC procedure;
2. Primary hepatocellular carcinoma or recurrent hepatocellular carcinoma which was previously treated with ablation or surgical resection only;
3. Scheduled for microwave ablation of the liver;
4. Performance status 0-2 (Eastern Cooperative Oncology Group classification);
5. Functional hepatic reserve based on the Child-Pugh score (Class A or B)
6. ASA score ≤ 3 ;
7. Has given voluntary, written informed consent to participate in this study and has authorized the transfer of his/her information to the Sponsor, and willing to comply with study-related evaluation and treatment schedule; and
8. At least 19 years of age.

8.2 EXCLUSION CRITERIA

Subjects will be excluded from the study for any of the following:

1. Active (subject currently receiving systemic treatment) bacterial infection or fungal infection;
2. Systemic administration (intravenous or oral) of steroids, including herbal supplements that contain steroids, within 30 days prior to the study procedure;
3. Chemotherapy or radiation therapy for hepatocellular carcinoma may not be performed for 30 days prior to the study procedure;
4. Subject with implantable pacemakers or other electronic implants;
5. Planned/ scheduled liver surgery;
6. Subject with a platelet count of less than 50,000/mm³;
7. Subject with an INR greater than 1.5;
8. Subject with renal failure on renal dialysis;
9. Scheduled concurrent procedure other than microwave ablation in the liver;
10. The subject is a female who is pregnant or breastfeeding;
11. Physical or psychological condition which would impair study participation;
12. Participation in any other clinical study concurrently or within the last 3 months;
13. The subject is judged unsuitable for study participation by the Investigator for any other reason; or
14. Unable or unwilling to attend follow-up visits and examinations.

8.3 PRIOR AND CONCOMITANT THERAPY

Excluding chemotherapy or radiation therapy (up to 30 days prior to procedure), study subjects may continue with their current medical care while in the study, including medications. All concomitant medications will be collected for this study.

8.4 SCREENING FAILURES

All subjects who have signed study consent but do not meet the inclusion/exclusion criteria and, therefore, have not initiated the study ablation procedure will be recorded as screen failures. The relevant electronic Case Report Form (eCRF) pages (demographics, reason for screen failure) will be completed for all screen failure subjects and, therefore, the data will be included in the study database.

8.5 REMOVAL OF SUBJECTS FROM STUDY

In accordance with the Declaration of Helsinki and Guideline for ICH and Korean GCP, a subject has the right to withdraw from the study at any time for any reason without prejudice to his/her future medical care by the physician or the institution. Should a subject (or subject's legally authorized guardian/representative) decide to withdraw, all efforts will be made to collect any adverse events they have experienced, if applicable.

Subject participation may be terminated prior to completing the study (i.e., the 3-year follow-up visit) for any of the reasons listed below (reasons that do not fit the categories below will be documented as "other"). Any adverse events which are ongoing at the time of discontinuation must be followed until resolution or until they become stable but ongoing. The relevant electronic Case Report Form (eCRF) pages (Study Exit, Adverse Event) will be completed for all withdrawn subjects and the data will therefore be included in the study database.

Subject Choice:

If a subject chooses to withdraw early from the study, the eCRF study completion page should be completed. When a subject's participation is terminated prior to completing the study, the reason for withdrawal is to be documented on the eCRF and in the source documentation.

Intra-treatment:

The Investigator must withdraw a subject during the procedure for one of the following reasons:

- Intra-treatment event that results in conversion to a surgical procedure or other procedure prior to the start of microwave ablation.

Post-treatment:

The Investigator must withdraw a subject after the procedure for one of the following reasons:

- **Concomitant medication/ procedure:**
 - Chemotherapy or radiation therapy for hepatocellular carcinoma may not be performed for 30 days after the procedure
- **Death:**
 - When possible, the cause of death will be documented.

- **Lost to follow-up:**

All subjects should be encouraged to return for protocol required clinic visits for evaluation during the study follow-up period. If a subject is unable to return for a clinic visit or unable to be contacted by telephone, attempts to contact the subject

should be documented in the source documents. Only after failing to contact the subject at the final follow-up visit, the subject will be considered lost to follow-up and the primary reason for early termination will be completed in the eCRF. Subjects who withdraw or are terminated early from the study will be replaced until 30 eligible subjects complete the 3-month visit after ablation (Visit 4).

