1. Mechanical probe breaks due to excessive force applied during probe placement, often through and around boney structures and/or cartilage.
2. Skin burns due to user placing probe improperly close to the patient's skin or delivering power for excess time and power given the probe placement.
3. Known risks associated with thermal ablation not associated with device failure or misuse.
4. Patient developed a bronchopleural fistula after a lung ablation procedure due to user error.

Regulatory Evidence of Substantial Equivalence

Additional information of the Certus 140 substantial equivalence may be found in the product's US FDA 510(k) clearance as below:

Product	FDA 510(k) Clearance
Certus 140 (including LK, LN and SR Ablation Probes	K100744
Certus 140 (including PR Ablation probes)	K113237
Certus 140 (SW Update to add Surgical SW)	K122217
Certus 140 (including CertuSurgGT Surgical Tool)	K130399
Ablation Confirmation SW Option	K160313
Certus 140 (including 15 ga probes)	K160936

4.3.2 Comparison with Radiofrequency Ablation Systems:

The subject assessments and procedure for microwave ablation (MWA) procedure being performed with the study devices are similar to the radiofrequency ablation (RFA) procedure that subjects would receive as part of their standard of care prior to the availability of MWA at the site.

To date, there is no reported difference in the reported adverse events between RFA and MWA.

In a meta-analysis by Huo et al⁴⁷, MWA and RFA had similar 1–5-year overall survival, disease-free survival, local recurrence rate, and adverse events. In terms of adverse events, MWA and RFA have similar low rates of complications, as identified in the same meta-analysis by Huo et al, and previous systematic reviews and multicenter trials^{18, 48} also found similar low rates of complications (4.1% for RFA and 4.6% for MWA).

4.3.3 Potential Benefit to Subjects:

The main benefits to Subjects from participation in this study are that they will be treated with a new microwave ablation technology, and the Sponsor will supply the study devices free of charge to the site who will treat the Subjects. There is no evidence that MWA is inferior to RFA but there is a strong suggestion that MWA is better for larger lesions^{12, 49}. As a result, subjects in the study may experience an improved result over standard of care treatment with RFA. The knowledge gained from this clinical trial may also help future microwave ablation patients.

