11.3 VISIT 2B- ABLATION

Data collected during procedure:

- Tumor details (size, type, location) and BCLC Staging (intra-procedure staging);
- Procedure details (ultrasound-guided):
 - Duration of procedure (first probe placement to last probe removal);
 - Duration of ablation;
 - Procedure performed;
 - Anatomical location of ablation;
 - Number of ultrasound scans performed for needle and margin assessment;
 - Number of needle placement attempts per needle;
 - Number of ablations;
 - Ablation settings (power and time);

Some of the above ablation procedure details will be provided to the site via a report generated from NeuWave Medical's Call Home Database. The study site will review the report and enter the procedure details into the clinical database, as applicable.

- Device accountability: Type(s) and no. of probes used;
- MRI and CT scans of the liver (up to 4 days after completion of procedure to confirm complete tumor ablation);
- All Adverse Events and SAEs (if applicable);
- Any update to concomitant medications.

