12.1.1.11 Reporting Adverse Events

Investigator's Responsibility:

The Investigator is required to report all AEs experienced by the subject from Visit 2B until the subject completes Visit 4 (3 months after the ablation procedure) or withdraws before Visit 4. All AEs during this time period, regardless of their relatedness to the study device(s) or procedure, must be reported in the AE eCRF within 2 weeks after the site becomes aware of the information. The investigator will evaluate the severity of the event, and its relatedness to the study device or procedure. Any necessary medical management of the event will be recorded in the subject's medical record/source document. All AEs must be followed until resolution or until they become stable but ongoing.

Sponsor's Responsibility:

The Sponsor will follow MFDS's guideline to report safety events related to the study medical devices with the timeline which is regulated by law.

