15.6 ANALYSIS SETS

There will be two primary analysis sets:

- The Full Analysis Set will be defined as all subjects in whom the microwave ablation procedure is completed and who provide information on ablation margins for evaluation

of Technical Success and Technique Efficacy. The Full Analysis Set will be the primary analysis population for summary of the primary endpoint and effectiveness-related secondary endpoints.

- The Safety Set will consist of all subjects in whom the microwave ablation procedure is attempted, i.e. started and regardless of whether it was completed as planned or not. The Safety Set will be the primary analysis population for all safety-related endpoints.

Additional analysis sets may be determined to be necessary (e.g. Per Protocol) pending trial progress and will be identified in the SAP as needed.

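### A subject converted before microwave ablation starts must be withdrawn on day 0, and reporting of new AEs and SAEs then stops, although complications are defined out to 30 days and beyond

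*Combined protocol and SAP*

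**What the plan says.** **Withdrawal.** Under its intra-treatment heading, section 8.5 states: "The Investigator must withdraw a subject during the procedure for one of the following reasons". The one reason listed is: "Intra-treatment event that results in conversion to a surgical procedure or other procedure prior to the start of microwave ablation". The same section adds: "Any adverse events which are ongoing at the time of discontinuation must be followed until resolution or until they become stable but ongoing". It also has the Study Exit and Adverse Event eCRF pages completed for every withdrawn subject. On replacement it says: "Subjects who withdraw or are terminated early from the study will be replaced until 30 eligible subjects complete the 3-month visit".

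**Reporting window.** Section 12.1.1.11 asks for all AEs "from Visit 2B until the subject completes Visit 4 (3 months after the ablation procedure) or withdraws before Visit 4". Section 12.1.1.12 sets the same limits for SAEs. Its later rule, for serious device effects, life-threatening events, deaths and related SAEs after Visit 4, likewise ends at withdrawal.

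**Complications.** Section 12.1.1.10 sorts complications into immediate (up to 6–24 hours), peri-procedural (within 30 days) and delayed (after 30 days). Ablation-related complications are to cover any problem in the 30-day period with any link to the procedure. They also cover later findings on imaging that are judged very likely due to the ablation.

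**Counting.** Section 15.6 says: "The Safety Set will consist of all subjects in whom the microwave ablation procedure is attempted, i.e. started", whether or not the procedure was completed as planned. Section 15.8.5 limits all summaries to subjects who undergo the ablation procedure and to observed data. Section 11.3 times the procedure from first probe placement and lists the duration of ablation separately. Under section 15.8.4, the first analysis is to describe safety out to 3 months.

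**The concern.** By timing procedure and ablation separately, the protocol recognises a phase in which a study probe has been placed but no energy has been delivered. Harm can arise in that phase. Section 4.3.1 lists among the known adverse events: "Mechanical probe breaks due to excessive force applied during probe placement". Section 4.3 also names bleeding, pneumothorax and collateral organ injury. It does not assign these to a phase, so it is an inference that they can arise at placement and lead to conversion, though a reasonable one.

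For a subject converted after such an event, the following weeks are when further complications would appear, and the reporting window has already closed. The subject did not choose to leave. The protocol imposes the withdrawal, so the loss of follow-up is avoidable. What is at stake is whether the 3-month safety profile is complete for the few subjects in whom the procedure went wrong earliest.

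**Working it through.** The plan has no figure of its own to reproduce. Section 15.7 gives at least 30 subjects without alpha, power or a precision target. The point rests on the text, and the arithmetic only shows scale.

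**Step 1. What remains reportable after a pre-ablation conversion.** Withdrawal happens during the procedure, so the window opened at Visit 2B closes the same day.

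| Event | Reportable as written? | Source |
|---|---|---|
| The event that forced the conversion | Yes; recorded and followed to resolution or stability | 8.5, 12.1.1.11 |
| Worsening or death as the outcome of that ongoing event | Yes, through the same duty | 8.5, 12.1.1.11 |
| New AE or SAE starting after withdrawal, within 30 days | No | 12.1.1.11, 12.1.1.12 |
| New delayed complication or death not arising from an ongoing AE | No; scheduled visits and imaging have also ended | 12.1.1.12, 8.5 |

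**Step 2. Compare with the complication definition.** The three time bands in 12.1.1.10 all extend past the end of the procedure. For a subject withdrawn during it, a new problem in any band falls outside the reporting window. A 30-day definition cannot be applied to a subject whose new events are collected only on day 0.

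**Step 3. Is the subject counted?** Section 15.6 turns on the *procedure* being started, and 11.3 counts the procedure from first probe placement. The more natural reading is that a subject with a probe placed is in the Safety Set. However, 15.6 does not define *started*, 8.5 speaks of the start of *ablation*, and 15.8.5 has a third wording. The inclusion is probable but not stated.

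**Step 4. Scale.** Let k be the number of such conversions in addition to 30 other treated subjects. The documents give no rate, so k is assumed.

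Share of the safety denominator with new-event follow-up cut at day 0, k/(30 + k):
- k = 1: 1/31 = 3.2%
- k = 2: 2/32 = 6.25%

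Chance of at least one conversion in 30 procedures, 1 − (1 − p)^30, for assumed p:
- p = 1%: 0.26
- p = 3%: 0.60
- p = 5%: 0.785

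Effect of one unreported new event of a given type, when the subject is in the Safety Set and no other subject has that event (exact Clopper-Pearson limits):
- captured: 1/31 = 3.2% (95% CI 0.1% to 16.7%)
- not captured: 0/31 = 0%, upper limit 1 − 0.025^(1/31) = 11.2%

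Effect if *started* were instead read as energy delivery, so that the subject is left out, again with no such event in the other 30:
- left out: 0/30 = 0%, upper limit 1 − 0.025^(1/30) = 11.6%
- counted, k = 1: 1/31 = 3.2% (0.1% to 16.7%)
- counted, k = 2: 2/32 = 6.25% (0.8% to 20.8%)

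**The case against.** The strongest reply is that the important harm is already captured. Section 8.5 itself requires ongoing AEs to be followed and the AE form completed, section 12.1.1.11 repeats the follow-up duty, and section 15.8.1 tabulates discontinuations with reasons, so a conversion is visible. A death that results from the original bleed is the outcome of a followed AE. Events after a conversion to surgery may also say little about microwave ablation. The study is descriptive, conversion before ablation may never happen, and the SAP still to be finalised could define *started*.

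Most of this stands, and it rules out several stronger readings that a reader might infer:
- *The injury leaves safety follow-up.* It does not; only new events after withdrawal do.
- *The injured subject is exchanged for an uninjured one in the safety result.* Replacement serves the count of 30 Visit 4 completers. It adds a subject and deletes nobody from the Safety Set, and nothing ensures that the added subject is free of injury.
- *The safety profile is necessarily biased favourably.* That needs a conversion followed by a new event, or the less natural reading of *started*. Neither is given.
- *One event decides the comparison with the literature.* Two large series cited in section 4.2 report major complications of 2.2% and 2.9%. Both figures lie inside the 0/30 and the 1/31 intervals, and the rates in Table 4 run from 0% to 24%.

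The reply does not answer the gap for new events. Following an ongoing AE is not the same as collecting a new one, and 12.1.1.10 counts problems with any link to the procedure, whatever follows the conversion. A definition in the SAP could settle who is counted, but it cannot recover events that the protocol told the site not to report.

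**Conclusion.** The point holds in a limited form. Followed as written, 8.5 together with 12.1.1.11 and 12.1.1.12 ends reporting of new AEs and SAEs on day 0 for a subject converted before ablation starts. This conflicts with the 30-day and delayed complication definition in 12.1.1.10, and it leaves the 3-month safety profile incomplete for that subject. Membership of the Safety Set is probable on the natural reading of 15.6 with 11.3, but the plan should say so.

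The likely size is small: 0 to 2 subjects, or 0% to 6.25% of the safety denominator. One missed event would change a rate for that event type from 3.2% to 0%, with widely overlapping intervals. This rests on an assumed number of conversions and on the inference that placement injuries can trigger them. It is a cheap improvement, not a flaw that undermines the study.

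**What to change.** 1. In 8.5, record a conversion before microwave ablation as study treatment not completed instead of study withdrawal. Alternatively, exempt it from the withdrawal cut-off in 12.1.1.11 and 12.1.1.12.
2. For these subjects, continue AE, SAE and survival collection to the Visit 4 time point. Contact or chart review is enough, and a subject's own right to withdraw is unaffected.
3. In 15.6, state that *started* means study probe placement attempted, in line with the procedure start in 11.3, and align 15.8.5.
4. Replacements may still count toward the 30 Visit 4 completers, with the converted subject kept in the safety denominator.

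This changes data collection and counting only, not clinical care. The cost is a few sentences of protocol wording and follow-up of probably 0 to 2 subjects (assumed). The reported complication rate may turn out slightly less favourable.

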8. Adverse Event and SAEs: Subjects will be assessed for safety from day of ablation through the 3-year follow-up. All AEs and SAEs will be reported from the day of the ablation up to 3 months after the ablation procedure. Expected serious adverse device effects (SADE), unexpected serious adverse device effects (USADE), life-threatening events, or events that result in death, and all SAEs with definite, possible, probable or unknown relationship to the study device or study procedure, will be reported from day of the ablation through the 3-year follow-up.
9. Unscheduled visits are only for those which are procedure, device or disease related.

NOTE:

- Subjects who have recurred at the target lesion or progressed with a new lesion following the first ablation, and are treated with any treatment post progression will be followed every 6 months (+/-28 days) from the day of the first ablation as a clinic visit or, if clinic visit is not possible, a phone contact visit (if a clinic visit is not possible). This will be called a "Reduced Follow-Up Schedule."

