11.10 REDUCED FOLLOW-UP VISIT

This visit can be a clinic visit or a phone contact visit which will occur every 6 months (+/-28 days) from the day of the first ablation. The following data will be collected only for subjects who have progressed or recurred following the first ablation and are retreated with any treatment post progression:

- Follow-up post-ablation treatment (if applicable);
- Any additional progression(s)/ recurrence(s);
- Survival status;
- Adverse Events (if applicable). Subjects will be evaluated for all adverse events according to the Investigator's standard of care practice during each follow-up visit. Note that for this study, after Visit 4 (3 months), only expected or unexpected serious adverse device effects, life-threatening events, events that result in death and all SAEs with definite, possible, probable or unknown relationship to the study device or study procedure will be reported to the Sponsor, if applicable;
- QOL questionnaires

For subjects on the Reduced Follow-up schedule 6 monthly visits occur until approximately 3 years post ablation.

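### Section 8.5 withdraws subjects given chemotherapy or radiation for HCC within 30 days of ablation, but the Table 1 note and Section 11.10 follow treated progressors to 3 years; in the narrow overlap, following 8.5 loses later outcomes.

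*Combined protocol and SAP*

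**What the plan says.** Section 8.5 (Post-treatment) reads "The Investigator must withdraw a subject after the procedure for one of the following reasons". The first reason listed is a restriction: "Chemotherapy or radiation therapy for hepatocellular carcinoma may not be performed for 30 days after the procedure". Death and loss to follow-up are listed after it. The same section opens in softer terms: "Subject participation may be terminated prior to completing the study (i.e., the 3-year follow-up visit) for any of the reasons listed below". It closes by saying that "Subjects who withdraw or are terminated early from the study will be replaced until 30 eligible subjects complete the 3-month visit". Section 15.8.5 repeats the replacement rule for terminations before 3 months and imputes nothing.

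The follow-up rules point the other way. Under the Table 1 note, subjects who recur at the target lesion or develop a new one and "are treated with any treatment post progression will be followed every 6 months". Section 11.10 applies to "subjects who have progressed or recurred following the first ablation and are retreated with any treatment post progression". It collects survival status and further progression, and says of its form: "This visit can be a clinic visit or a phone contact visit". On duration it says: "For subjects on the Reduced Follow-up schedule 6 monthly visits occur until approximately 3 years post ablation". Neither passage excludes treatment given in the first 30 days.

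Three analysis rules determine the consequences. Section 15.6 requires margin information for both Technical Success and Technique Efficacy for entry to the Full Analysis Set. Section 15.8.3 limits the local tumor progression (LTP) analysis to subjects observed at the time point, and summarizes 36-month progression-free survival (PFS) and overall survival similarly. Section 12.1.1.11 ends adverse event (AE) reporting at withdrawal if that comes before Visit 4.

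**The concern.** For the same subject, one rule ends study participation and the other continues it for about 3 years. The site could follow either.

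The choice is unlikely to be neutral. Further HCC therapy soon after ablation is more likely when disease is not controlled, so withdrawn subjects would plausibly do worse than those who stay. Replacing them with subjects who reach 3 months, and summarizing observed data only, would then tend to make the reported rates look better. In a study of about 30 subjects meant for comparison with published series (Section 15.7), one to three unknown outcomes matter.

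**Working it through.** The plan gives no figure to reproduce. Section 15.7 sets at least 30 three-month completers with no hypothesis, and no document gives an expected number of such withdrawals. The check is therefore textual first, then a sensitivity calculation.

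**1. Which rule applies to whom**

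- Progression recorded, then chemotherapy or radiation for HCC by day 30: 8.5 says withdraw; the Table 1 note and 11.10 say follow. Both apply.
- The same therapy by day 30 without recorded progression: only 8.5 applies. There is no contradiction, only an avoidable loss of data.
- Repeat ablation, or chemotherapy or radiation after day 30: not a reason for withdrawal in 8.5.

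**2. What is lost if 8.5 is followed**

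- *Technical Success reading:* normally safe, because the scans are due within 4 days of ablation (Section 9.1).
- *1-month Technique Efficacy:* lost if not yet read. Visit 3 is at 1 month ± 14 days (Section 15.3). Taking a month as 30 days, that is day 16 to day 44, so withdrawal by day 30 can come first. If progression was found on the Visit 3 scan, the reading already exists.
- *Adverse events:* ongoing events are still followed (Section 8.5), but reporting of new events to Visit 4 stops (Section 12.1.1.11). Safety Set membership is unaffected.
- *LTP and PFS:* later events are lost unless already recorded. In the two-rule group the PFS event is recorded, and the LTP event too if the progression was local.
- *36-month survival status:* lost.
- *Full Analysis Set:* Section 15.6 names both readings. Read literally, a subject without the 1-month reading may leave the set used for the primary endpoint.

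**3. Size for 36-month survival**

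Assume k subjects with unknown status and 30 others fully observed, of whom s are alive. Worst case = s/(30+k); best case = (s+k)/(30+k); width = k/(30+k). Two values of s are used: 22/30 = 73.3%, near the 73% at 3 years cited in Section 4.2 for a 1007-patient series, and 18/30 = 60.0%, the 3-year figure cited there for 3–5 cm HCC.

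| k | Width (points) | s = 22: worst / best | s = 18: worst / best |
|---|---|---|---|
| 0 | 0 | 73.3% / 73.3% | 60.0% / 60.0% |
| 1 | 1/31 = 3.2 | 22/31 = 71.0% / 23/31 = 74.2% | 18/31 = 58.1% / 19/31 = 61.3% |
| 2 | 2/32 = 6.3 | 22/32 = 68.8% / 24/32 = 75.0% | 18/32 = 56.3% / 20/32 = 62.5% |
| 3 | 3/33 = 9.1 | 22/33 = 66.7% / 25/33 = 75.8% | 18/33 = 54.5% / 21/33 = 63.6% |

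The width is not a shift. From 73.3%, the shift at k = 3 lies between −6.7 and +2.4 points; from 60.0%, between −5.5 and +3.6.

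Kaplan-Meier estimation does not recover the loss. With k subjects censored at day 30, before the first of 8 deaths, the estimate stays at 22/30 = 73.3% for k = 0 to 3.

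**4. Size for 1-month Technique Efficacy (conditional)**

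Suppose the k subjects were failures whose reading was never taken, and all 30 others succeeded. The report would show 30/30 = 100% (exact 95% interval 88.4–100). With the k counted it would be 30/31 = 96.8% (83.3–99.9), 30/32 = 93.8% (79.2–99.2) or 30/33 = 90.9% (75.7–98.1). The same arithmetic applies to Technical Success only if the subjects also leave the Full Analysis Set and were failures on the first scan.

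**5. The sentence in 15.8.3**

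If one recorded progression is dropped because the subject has no 36-month observation, an assumed PFS of 12/31 = 38.7% is reported as 12/30 = 40.0%.

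**The case against.** The list in 8.5 may simply record reasons for exit. It includes death and loss to follow-up, which no investigator chooses to apply, and the section opens with permissive wording. This has some force but does not settle the matter. Death and loss to follow-up end observation by themselves; receiving chemotherapy or radiation does not, and a site that takes the mandatory sentence at its word stops following someone it can still reach.

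A specific 30-day rule could also be read as overriding a general follow-up rule. Nothing in the documents says so, and Visit 3 already collects post-ablation treatment (Section 11.5).

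The narrowness of the overlap is conceded. It needs progression and restricted therapy both by day 30, in a single-lesion, BCLC Stage A population. Residual tumor on the first scans is classed as incomplete ablation, which is not clearly recurrence or progression, so such subjects may fall under 8.5 alone. The study is descriptive, and even the −6.7 point shift lies inside the exact 95% interval for 22/30 (54.1–87.7%). That interval describes sampling error, however, and does not cover an informative loss. The Kaplan-Meier result holds by construction; it shows only that the method gives no protection here. The 15.8.3 sentence reaches well beyond these subjects and would need attention anyway.

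A reader might infer that the main loss is 36-month survival status. The documents do not support that ranking, because the 1-month reading, new AE reporting and possibly Full Analysis Set membership can go as well. Nor do they support saying that the primary endpoint is necessarily affected: that depends on the literal reading of 15.6.

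**Conclusion.** The contradiction is real for subjects who progress and receive chemotherapy or radiation for HCC by day 30, and the passages must be reconciled. For subjects given such therapy without recorded progression, continued observation is a design improvement and not the repair of a contradiction. A reader might also infer that 8.5 removes everyone treated after progression; it does not, since it covers two kinds of therapy in one 30-day period.

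The size is unknown because the number affected is unknown. With k = 1 to 3 assumed and 30 others fully observed, crude 36-month survival carries a worst-to-best range of 3.2 to 9.1 points; with k = 0 there is no effect. That the loss is informative is plausible but not shown by the documents. The change is worth making because it is cheap and the study small. Confidence is medium.

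**What to change.** **Protocol.** Reconcile 8.5 with the Table 1 note and 11.10 so that receiving off-protocol therapy does not by itself end study observation. This leaves the 30-day restriction and every treatment rule as they are. Ablated subjects who have not withdrawn consent stay under outcome and AE follow-up: retreated progressors on the existing Reduced Follow-Up Schedule, others on the regular visits with CT. The reduced visit may be by phone and lists no CT, so it would not allow LTP to be assessed in the second group. Its first contact falls at 6 months, so the text should say that AE reporting to the 3-month point continues for retreated progressors.

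**Analysis.**
- In 15.6, state that an ablated subject with a Technical Success reading stays in the Full Analysis Set even if the 1-month reading is missing. This is needed in any case, because the reduced schedule would not supply that reading.
- State that replacement does not remove a subject from the denominator. Replacement to reach 30 three-month completers can continue.
- In 15.8.3, replace the restriction to subjects observed at the time point with standard Kaplan-Meier handling: count recorded events and censor other subjects at last assessment.

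**Cost.** Wording, plus at most 6 reduced contacts (months 6 to 36) or 9 regular visits (Visits 3 to 11) per affected subject, all of types already planned. Reported rates may be slightly less favorable.
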